## 3.6.2 Laboratory, ECG, and Vital Signs Data

Assessments will be assigned to cycles based on the collection date of the sample relative to the start dates of the cycles from the study drug administration page.

Baseline assessments will be considered as those data collected:

- Within 28 days prior to first day of study drug and
- The closest non-missing data value assessment prior to the first dose date

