-  Seribantumab PK: all patients; in relation to seribantumab infusion
  - a C1W1: immediately after the end of the Seribantumab infusion (+15 mins)
  - b C1W3, C2W1, C2W3: pre-dose
-  Immunogenicity samples should be collected for all patients prior to dosing.
-  In the event a patient experiences an infusion reaction at any point in the study, an anti-Seribantumab antibody assay will be taken within 24 hours of the event, in addition to the scheduled time-points. For patients who experience a Grade 3 or 4 infusion reaction to Seribantumab, an anti-Seribantumab antibody titer will be taken as close to the onset of the infusion reaction as possible, at the resolution of the event and 28 days (+/- 2 days) following the event.
-  Disease evaluation per RECIST version 1.1.
-  Tumor sample is to be collected for all HRG positive patients that receive HRG results for eligibility based on testing of archived samples. An additional sample is not required for patients who underwent a fresh biopsy for eligibility testing.
-  Fulvestrant PK: all patients: prior to seribantumab injection
-  Serum for biomarkers should be collected pre-infusion on week 1 of each cycle for all patients
-  End of treatment (30-day Follow-up) visit should be completed within 30 days of the last dose of study drug
-  Should patients refuse or drop out of survival follow-up, attempts should be made to obtain any death information available via public records.
-  One reading prior to infusion with seribantumab.
-  AE/SAE collection to be included. S/AE assessment and reporting will proceed as outlined in Sections 9.2 and 9.3
-  All patient hospitalizations and/or hospital visits should be collected, whether or not associated with an adverse event.
-  In addition to the timepoints noted, MUGA or Echocardiogram should be performed post-screening for any study patient who develops symptoms consistent with new onset of congestive heart failure.
-  Unless performed within the last 4 weeks as part of assessments in the previous cycle
-  Sample to be collected prior to any study treatment.

Proprietary and Confidential Page 44 of 65

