# 7.5. Electrocardiogram (ECG)

A 12-lead electrocardiogram (ECG) will include a description of the cardiac rate, rhythm, interval durations, and an overall impression. QTc should be calculated using the Fridericia method (QTcF). ECGs will be performed for all patients at screening to rule out clinically significant abnormalities. For randomized patients, ECGs will be performed on week 1 of each cycle prior to dosing with seribantumab.

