#### 3.8 Covariates

Baseline evaluations are those collected within 28 days prior to the start of treatment. If more than one baseline evaluation is available, select the closest non-missing value prior to first dose. The closest non-missing observation may be selected on the day of cycle 1 day 1 if study procedures are indicated prior to dosing.

The following baseline characteristics will be included as covariates which may be included in model testing exercises: Age, gender, race, ethnicity, primary diagnosis and time from primary cancer diagnosis to randomization, time since last prior systemic treatment, investigative site, and others may be identified.

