## 5.6.3 Laboratory Evaluation

Laboratory analytes will be summarized according to panel (i.e., hematology, chemistry, urinalysis).

Shift in laboratory analyte grade will be characterized by worst from baseline and at end of treatment. Shift categories will include normal grade 1 to grade 5 and totals. Percentages will be based on the number with baseline and postbaseline values for that particular analyte.

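### SAP 3.6.2 bars a Cycle 1 Day 1 pre-dose ECG from serving as baseline, conflicts with SAP 3.8, and does not keep that reading out of the ECG outlier counts

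*SAP*

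**What the plan says.** SAP 3.6.2, the section written for laboratory, ECG and vital-sign data, sets two conditions for baseline: "Within 28 days prior to first day of study drug and" "The closest non-missing data value assessment prior to the first dose date". It also gives the cycle rule: "Assessments will be assigned to cycles based on the collection date of the sample relative to the start dates of the cycles". Both rules work on dates, and neither mentions clock time or a pre-dose sample on the first dosing day.

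SAP 3.8 (Covariates) has the same 28-day window but adds: "The closest non-missing observation may be selected on the day of cycle 1 day 1 if study procedures are indicated prior to dosing". The SAP does not say which section governs a variable that falls under both.

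Protocol 7.5 fixes the timing of the ECG: "For randomized patients, ECGs will be performed on week 1 of each cycle prior to dosing with seribantumab". A footnote to the schedule in Protocol 6.1 agrees: "One reading prior to infusion with seribantumab". The schedule also places vital signs, blood count, chemistry and coagulation in Cycle 1 Week 1, but does not time them against the infusion.

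For the outputs, SAP 5.6.3 says: "Shift in laboratory analyte grade will be characterized by worst from baseline and at end of treatment". The categorical analysis in SAP 5.6.5 counts QTcF rises from baseline above 30 and 60 msec, with similar rules for PR, QRS and heart rate. Neither passage restricts the values counted to those taken after dosing.

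**The concern.** The most recent drug-free reading is usually the best baseline. Under 3.6.2, an ECG taken on the first dosing day before the infusion is passed over for an older screening ECG, whereas the same ECG taken one day earlier would be baseline. Its collection date then puts it in Cycle 1. Since the outlier text has no post-dose limit, a value that study drug cannot have influenced can be counted as a rise from baseline.

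The two SAP sections also allow two programmers to derive different baselines for the same patient. At stake are the accuracy of the ECG outlier tables and, possibly, the laboratory shift tables. Some patients could also lose their ECG baseline although a valid pre-drug reading exists.

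**Working it through.** The plan states no figure on this point, so there is none to reproduce. The check applies the rules literally and then gauges the size.

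**1. Trace of the rules.** Day 0 is both the first dose date and the start of Cycle 1. SAP 3.6.2 accepts days −28 to −1. SAP 3.8 accepts days −28 to 0 when the day 0 procedure is scheduled before dosing.

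| Readings on days | Baseline, 3.6.2 | Baseline, 3.8 | Label of last reading |
|---|---|---|---|
| −7 and 0 | −7 | 0 | Cycle 1 |
| −1 and 0 | −1 | 0 | Cycle 1 |
| −7 and −2 | −2 | −2 | before Cycle 1 |
| 0 only | none | 0 | Cycle 1 |

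The third row is a week 1 reading taken early within the ±2-day visit window of Protocol 6.1. The rules then agree and no problem arises.

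**2. When the last row can occur.** Protocol 6.1 ties the screening ECG to 28 days around main consent, not to first dose. First dose may follow randomization by up to 7 days. If randomization fell 28 days after consent (an assumption) and the ECG was done on the day of consent, the gap could reach 28 + 7 = 35 days, outside the 28-day window. The only ECG that could then serve is the one on Day 1, which 3.6.2 rejects. The documents do not show how often this would happen. Screening vital signs and bloods are due within 7 days of first dose, so they do not face this gap.

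**3. Share of ECG slots.** Assume treatment lasts as long as the median PFS in Protocol 10.2, with one ECG every 28 days from day 0.
- 4 months = 4 × 30.4375 = 121.75 days: ECGs on days 0, 28, 56, 84 and 112, so Day 1 is 1 of 5 (20%).
- 7 months = 213.06 days: ECGs on days 0 to 196, so Day 1 is 1 of 8 (12.5%).

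These are shares of time points, not changes in any reported result.

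**4. False QTcF rises on the Day 1 reading.** The documents give no within-patient SD. Assume s = 10 ms (range 8 to 12), normal errors and no drug effect.
- Baseline is one reading: the difference has SD s√2 = 14.14, and P(Z > 30/14.14) = P(Z > 2.12) = 1.7%. For s = 8 and 12 the result is 0.4% and 3.9%.
- Baseline is the mean of the two screening readings, taken as independent: SD s√1.5 = 12.25, and P(Z > 30/12.25) = P(Z > 2.45) = 0.7%.

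Protocol 6.1 requires two screening readings only five or more minutes apart, so full independence is generous and 0.7% is the low end for s = 10. The SAP does not say how the two are combined.

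**5. Net effect on the outlier table.** Some of these patients would cross 30 ms on a later ECG anyway. With a single-reading baseline error b ~ N(0, 10²) and n on-study ECGs, the chance of at least one false outlier is 1 − E[Φ((30 + b)/10)ⁿ]. Dropping the Day 1 reading takes n from 5 to 4 and the chance from 6.5% to 5.5%, or n from 8 to 7 and the chance from 9.0% to 8.2%. The reduction is 0.8 to 1.0 percentage points, at most 0.010 × 80 = 0.8 of a patient.

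**The case against.** The other side has four good arguments.

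First, the SAP never says that a Cycle 1 label means on-treatment. A reader might infer that every pre-drug Day 1 reading will be reported as an on-treatment safety result. The documents do not support that in general: the table of out-of-range vital signs in SAP 5.6.4 is limited to the treatment period. The inference is reasonable only where no limit is stated, as in the ECG outlier counts and the laboratory shifts.

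Second, a reader might infer that one contrast in the QTcF by-timepoint model would have a true effect of zero. SAP 5.6.5 describes the repeated measures in that model as post-dose, and a pre-dose Day 1 ECG is not one of them.

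Third, only the ECG is documented as pre-dose. With sample times unstated for bloods and vital signs, a date rule is a defensible conservative choice, and any older baseline for these is at most about a week old.

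Fourth, the SAP names another protocol number and describes a phase 3 design in which ECG effects are an objective, unlike this protocol. Applying this protocol's ECG schedule to its QTcF analyses is therefore uncertain.

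All four narrow the point. None removes the conflict between 3.6.2 and 3.8, or the fact that the stated ECG rule discards a reading the protocol requires before dosing.

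**Conclusion.** The point holds for ECG. Read literally, 3.6.2 excludes a Day 1 pre-dose ECG as baseline, the cycle rule files it under Cycle 1, and nothing removes it from the outlier counts. The covariate exception in 3.8 points the other way without clearly overriding 3.6.2. A patient whose screening ECG falls outside the 28-day window would have no ECG baseline. For laboratory shifts and vital signs the point is conditional on Day 1 measurements being taken before dosing.

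The size is small. The per-patient figure of about 0.7% to 1.7% rests on an assumed QTcF SD of 10 ms and normal errors, and the net change in patients flagged is under one in 80. The mechanism adds pre-drug noise equally in both arms, so it is not expected to favour either. Only safety summaries are affected; the primary PFS analysis, its error rate and its power are not. The change is worth making because the current text replaces the best pre-drug value with an older one, or with none.

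**What to change.** Use one baseline definition in SAP 3.6.2 and 3.8: the last non-missing value before the first administration of study drug, within the existing 28-day window, including Cycle 1 Day 1 values that are timed before dosing or, where no clock time is recorded, scheduled before dosing. Add that these pre-dose Day 1 values are not post-baseline values and do not enter the shift, outlier or by-timepoint summaries.

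The cost is SAP wording and derivation code. No new data, visits or protocol change are needed, and the SAP must in any case be aligned with this protocol.

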#### **3.7** Stratification Factors

Randomization will be stratified based on the following prognostic factors:

- Prior chemotherapy for locally advanced or metastatic disease (yes, no)
- Chemotherapy backbone (exemestane or fulvestrant)
- Geographic Region (US, Non-US/Non-Asia, Asia)

#### 3.8 Covariates

Baseline evaluations are those collected within 28 days prior to the start of treatment. If more than one baseline evaluation is available, select the closest non-missing value prior to first dose. The closest non-missing observation may be selected on the day of cycle 1 day 1 if study procedures are indicated prior to dosing.

The following baseline characteristics will be included as covariates which may be included in model testing exercises: Age, gender, race, ethnicity, primary diagnosis and time from primary cancer diagnosis to randomization, time since last prior systemic treatment, investigative site, and others may be identified.

#### 3.9 Biomarkers

Baseline serum and tissue samples will be collected. Continuous and categorical type of biomarkers may be available. For continuous biomarkers, the value at and above the median will be used to determine the high group, while the low group is below. Categorical parameters will be classified into a maximum of three groups. Additional analyses will be considered exploratory in nature. Samples will be used to assess additional clinically relevant biomarkers, including but not limited to expression levels of the ErbB3 receptor, cMET, IGF-1R, and FGF receptor tyrosine kinases and will include assessment of their respective ligands (e.g. HGF, FGF-2, IGF-1, and IGF-2 mRNA or protein).

The only biomarker detailed in this SAP will be HRG positive as per the primary efficacy population analysis.

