## 4.3.2. Implementation of HRG RNA-ISH Testing

The HRG RNA-ISH assay can be used to measure mRNA expression on tissue slides obtained from formalin-fixed paraffin embedded archived blocks, core biopsies or fine needle aspirates; therefore, any of these methods of collection is acceptable for testing. Formalin-fixed clinical trial specimens will be submitted directly by clinical sites to the designated CLIA certified central lab. Full details regarding collection, processing and shipment of samples are outlined within the study lab manual.

The central lab will process the samples and provide the stained slides to a trained pathologist to assess tumor content and percentage of tumor cells expressing HRG mRNA. The pathologist will assign scores of 0, 1+, 2+, or 3+ based on HRG mRNA staining. Samples scored at  $\geq$  1+ will be considered HRG positive, and samples scored at 0 will be considered HRG negative. This result will be communicated back to the investigative site within 7 days of sample receipt at the central lab.

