# 10.2. Statistical Hypothesis and Determination of Sample Size

The primary hypothesis is to test for differences in progression-free survival (PFS) distributions.

A stratified log-rank test will be used to analyze PFS differences with the stratification factors in the model: Statistical significance will be determined by using a one-sided type I error of 0.10. A stratified Cox proportional hazards model will be used to estimate the hazard ratio using geographic region (US, non-US) and bone-only disease (yes, no) as stratification factors.

The median PFS for the control arm (fulvestrant + placebo) is assumed to be 4.0 months in this patient population. A total of 58 PFS events will be required across two treatment arms randomized in a 1:1 ratio giving 80% power to detect a hazard ratio (HR)  $\leq$  0.57 (mPFS: 4 v 7), assuming a 1-sided significance level of 0.10. Approximately 200 patients will need to be screened in order to accrue 80 randomized in approximately 16 months with a total study duration of 20 months.

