## 5.5.4 Exploratory Biomarker Analysis

Descriptive statistics will be used to characterize the biomarkers within treatment groups over time. Continuous markers will be summarized using the change from baseline and observed values. Change from baseline to last observed will be analyzed using an ANCOVA model with baseline and stratification factors, treatment as fixed effects. Interaction effects may be tested and included in the final model(s) if deemed important. Least squares means and 95% confidence intervals will be reported. Categorical markers will be summarized using shift from baseline to last observed. CMH test using stratification factors will be used to analyze parameters.

The biomarker relationship to outcomes OS and PFS will be analyzed using a stratified log-rank test. Screening values of biomarker values will be used in the following analysis. Continuous biomarker values will be dichotomized by  $\geq$  median, < median; as well as quartiles. Biomarker analyses will consist of performing analysis on the overall PFS endpoint. Kaplan-Meier displays will be reported. Kaplan-Meier curves will include the following:

- seribantumab, Control According to categorical grouping
- Control Only According to categorical grouping

Included in the graphs will be hazard ratio and 95% confidence intervals, median PFS and 95% confidence intervals, number and percentage of events and censors. These will be performed for all markers identified. Forest plots will be used to describe the biomarker subgroups relationship via hazard ratios and 95% confidence intervals.

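### The only fully specified link between continuous biomarkers and PFS or OS is a median or quartile split, and no analysis by HRG score is planned (exploratory analyses only)

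*SAP*

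**What the plan says.** **Continuous markers.** SAP 3.9 gives the grouping rule: "For continuous biomarkers, the value at and above the median will be used to determine the high group, while the low group is below". SAP 5.5.4 takes screening values, tests their relationship to OS and PFS with a stratified log-rank test, and repeats the rule ("Continuous biomarker values will be dichotomized by" the median), adding quartiles. It also plans Kaplan-Meier curves by group and forest plots of hazard ratios by biomarker subgroup.

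**Other text that touches markers.** SAP 5.5.2 lists a stepwise evaluation of baseline covariates and biomarker factors for PFS, and Cox models with treatment, covariate and their interaction. SAP 5.3.2 explores treatment-by-covariate effects for factors that survive selection. Neither says on what scale a marker enters. SAP 5.5.4 also has an ANCOVA of change from baseline, in which the marker is the response. Protocol 10.5.5 foresees Cox models for biomarkers and leaves the detail to the SAP.

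**HRG.** SAP 3.9 says: "The only biomarker detailed in this SAP will be HRG positive as per the primary efficacy population analysis". Protocol 4.3.2 has the pathologist "assess tumor content and percentage of tumor cells expressing HRG mRNA" and assign a score of 0, 1+, 2+ or 3+. SAP 2.1 lists positive scores from 1+ to 4+. SAP 3.9 allows categorical markers up to three groups.

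**The concern.** Protocol 8.7.2 to 8.7.4 collect tissue, serum and plasma to find markers that help predict or evaluate response to seribantumab. Prediction is a treatment-by-marker question, usually about a graded effect. A split at the sample median treats every patient on one side of the cut as alike, so it tests a graded effect inefficiently. The cut-point also moves with the sample and is hard to carry into another trial. SAP 5.5.4 itself contains no treatment-by-marker test for PFS or OS.

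For HRG, a variable that is positive for everyone in the analysis set cannot be related to outcome there. Whether benefit rises with HRG level matters for this drug. The earlier breast cancer result (Protocol Table 1) rests on 21 HRG-positive patients classified by RT-PCR on archived tissue, whereas this trial selects at an ISH score of 1+ or more. In the HRG-negative subgroups of the three earlier trials the hazard ratios were 1.06, 1.54 and 2.43 (Protocol Table 2). The plan has no analysis that would show a gradient.

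**Working it through.** **Step 1. Event count.** Protocol 10.2: "A total of 58 PFS events will be required across two treatment arms randomized in a 1:1 ratio"; the target is HR "0.57 (mPFS: 4 v 7), assuming a 1-sided significance level of 0.10", with 80% power. Schoenfeld: D = 4(z₀.₉₀ + z₀.₈₀)² / (ln HR)² = 4(1.2816 + 0.8416)² / (ln 0.57)² = 18.03 / 0.316 = 57.1, so 58. With HR = 4/7 it is also 58. The 58 reproduces. The SAP's own count is 195 events at 2:1 and one-sided 0.025 (SAP 5.1). Schoenfeld gives 186 for 95% power at HR 0.57, and 195 events give 95.9%, which agrees with the SAP's claim of at least 95%. Neither document states power for the biomarker analyses.

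**Step 2. Information kept by grouping.** For a log-linear effect, the fraction kept is the squared correlation between the marker and its group means. For a standard normal marker cut at the median the group means are ±√(2/π), so the fraction is 2/π = 0.637:
- 58 × 0.637 = 36.9 effective events (36% lost)
- 195 × 0.637 = about 124 effective events

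The documents give no marker distribution, so the range is:

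| Marker shape (assumed) | Median split keeps | Of 58 events | Quartile groups keep | Of 58 events |
|---|---|---|---|---|
| Uniform | 0.750 | 43.5 | 0.937 | 54.4 |
| Normal | 0.637 | 36.9 | 0.860 | 49.9 |
| t, 5 df | 0.540 | 31.3 | 0.759 | 44.0 |
| Lognormal, σ 0.5 | 0.517 | 30.0 | 0.753 | 43.7 |
| Exponential | 0.479 | 27.8 | 0.734 | 42.6 |
| Lognormal, σ 1 | 0.271 | 15.7 | 0.475 | 27.6 |

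The skewed rows take the effect as linear in the untransformed value. If it is linear in the log, a lognormal marker returns to the normal row.

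**Step 3. Power for a prognostic effect** (58 events, normal marker, two-sided 0.05). For one-degree-of-freedom tests, power = Φ(√D·b − 1.96), where b is the log HR per SD and D the effective events. At HR 1.5 per SD, b = 0.4055:
- continuous: √58 × 0.4055 − 1.96 = 1.13, power 87%
- median split: √36.9 × 0.4055 − 1.96 = 0.50, power 69%
- quartile trend: √49.9 × 0.4055 − 1.96 = 0.90, power 82%
- unordered quartile test: 3 df, non-centrality 49.9 × 0.4055² = 8.2, power 67%

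In the same order, power is 52%, 36%, 46% and 31% at HR 1.3, and 98.9%, 92.5%, 97.7% and 92.8% at HR 1.75.

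A Cox score-test simulation (80 patients, 58 events, 3,000 runs) gave 84% continuous, 63% median split and 62% unordered quartiles at HR 1.5. Under the null the rejection rates were 5.5%, 5.3% and 6.7%. The ratio of median-split to continuous information was 0.64 at HR 1.5 and 0.65 at HR 1.75.

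**Step 4. Treatment-by-marker effect.** A simulation on the protocol's design (80 patients 1:1, control median 4 months, HR 0.57, 16-month accrual, cut at 58 events, normal marker, two-sided 0.05, 1,500 runs) gave 80% power with a continuous term and 56% with the split, for an interaction of 0.8 in log HR per SD. That is a ratio of hazard ratios of e^0.8 = 2.2 per SD: a large effect, chosen for illustration. The simulation is not stratified.

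**Step 5. HRG.** SAP 2.1 keeps only HRG-positive patients in the primary efficacy set. Protocol 10.3 keeps only patients confirmed positive on fresh tissue in the per-protocol set. In both sets HRG positivity has no variance, so no efficiency figure applies to it. The score does vary among positives, but the documents do not give its distribution, so the power of a trend test cannot be computed.

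**The case against.** - **A reader might infer that continuous markers are analysed only by splitting.** The documents do not support that. SAP 5.5.2 puts biomarker factors into PFS models without calling for a split and plans covariate interactions, and SAP 5.5.4 has an ANCOVA on the marker's own scale. What stands is that the scale in 5.5.2 is unstated, the only rule the SAP gives is the split, and in the ANCOVA the marker does not predict outcome.
- **A reader might infer that a third of the information is lost whatever is done.** For a normal marker a quartile trend loses only about 14%. However, 5.5.4 specifies a log-rank test and no trend, and the unordered test has about the median split's power. If the truth were a threshold exactly at the median, the split would lose nothing and a straight-line term would keep only 64%, by the same correlation.
- **A reader might infer that HRG is constant throughout the trial and its grading ruled out.** It is constant only in the two sets named in Step 5. Both documents allow for randomized patients outside them, and SAP 3.9's three groups would fit 1+/2+/3+. Graded analysis is unplanned, not excluded. Percentage of positive cells is assessed, but only the score is described as the assigned result.
- **The 58 events and the split rule come from different designs.** The SAP names another protocol number and a phase 3 trial with exemestane or fulvestrant. This is a fair objection to any absolute count; the proportional loss does not depend on it.
- **These analyses are exploratory, and splines or many interactions would overfit at this event count.** Both points stand. They limit the weight of the concern and the ambition of the fix.

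**Conclusion.** The concern holds in a limited form. For continuous markers, the one outcome analysis that the SAP spells out is a log-rank test on sample-median or quartile groups. Under a normal marker and log-linear effect the median split costs 36% of the information (58 events to about 37, or 195 to about 124). Across the other assumed shapes the cost is 25% to 73%, and it is smaller for a threshold effect near the cut. These distributions are assumptions, not figures from the documents. The percentage does not apply to HRG: positivity carries no information where everyone is positive, and analysis by score is simply not planned. It would be wrong to read this as a threat to the primary result. The primary PFS comparison does not use these groups, so the change is a worthwhile, inexpensive improvement to exploratory work.

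**What to change.** 1. In SAP 3.9 and 5.5.4, and for biomarker factors in 5.5.2, state that continuous markers enter the stratified Cox model on a continuous scale (for example log), with a treatment-by-marker term and a check of linearity.
2. Add an ordinal trend over the HRG score (1+/2+/3+) by treatment. State which specimen's score is used, archived or fresh, and reconcile the 1+ to 4+ list in SAP 2.1 with the 0 to 3+ scale in Protocol 4.3.2.
3. Keep median and quartile groups for Kaplan-Meier display.
4. Label the results exploratory and report how many markers were tested.
5. Separately, reconcile the SAP's design (195 events, 2:1, different protocol number) with the protocol's 58 events at 1:1.

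For items 1 to 4 the cost is SAP wording and a little programming before database lock; the HRG score needs no new data. The downsides are an assumed linear shape, which the check addresses only in part, and limited room for splines or many interactions with this number of events.
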